#### 10.3.3.2. Secondary Analyses

The incidence (percent of patients with at least 1 event) of infusion set failures, as defined in the primary objective, premature infusion set changes by reason, and severe hypoglycemia will be analyzed using Prescott's exact test.

Similarly, Wilcoxon signed-rank test will be used to analyze the rate of infusion set failures, premature infusion set changes by reason, and severe hypoglycemia, as described in Section [10.3.3.1](#).

As an additional analysis, the rate and incidence will be determined for infusion set failures leading to premature infusion set changes due to unexplained hyperglycemia with blood glucose >250 mg/dL that does not decrease by >50mg/dL within 1 hour following a correction bolus delivered via the pump and analyzed in the same way as described for the primary endpoint.

For infusion set failures defined in the primary objective and premature infusion set changes, the number of events and the number of patients with events will be derived for each treatment group by infusion set catheter dwell time ( $\leq 24$  hours,  $>24$  and  $\leq 48$  hours,  $>48$  and  $\leq 72$  hour,  $>72$  hours), and overall (across over the course of approximately 72-hours of continuous infusion).

Other safety measures will include AEs, hypoglycemia, vital signs and weight, treatment exposure, laboratory measures, and antibodies to insulin lispro. Analyses will be performed on data collected over the 6-week treatment period for each treatment group.

Events that are newly reported after the first dose of IP or reported to worsen in severity from baseline will be considered TEAEs. The Medical Dictionary for Regulatory Activities (MedDRA) lowest level term (LLT) will be used in the treatment-emergent assessment. The maximum severity for each LLT during the baseline period will be used as baseline severity.

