#### **10.3.3.3. Tertiary/Exploratory Analyses**

Continuous variables and the change from baseline for these variables will be analyzed by the MMRM models as described in Section 10.3.1. Categorical variables will be analyzed either by model (for example, a generalized linear mixed model) or nonparametric methods (for example, Wilcoxon signed-rank test or Prescott's exact test).

To assess the glucose control over the course of approximately 72-hours of continuous infusion, the duration and percentage of time in ranges (target, hypoglycemia or hyperglycemia) and incremental AUCs after breakfast, will be derived based upon the CGM raw data collected on Day 1, Day 2, and Day 3 of infusion set catheter wear and summarized by treatment group.

Analysis details for the tertiary endpoints will be described in the SAP.

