6.11.2. Other Secondary Safety Analyses

The analyses described in Section 6.11.2 will include data collected for the Safety Population including data collected prior to permanent discontinuation (i.e., last dose) of IP in each 6-week treatment period. In addition, other than severe hypoglycemia events, all secondary safety endpoints are pump-related, and therefore the corresponding analyses will also exclude data (if any) that are collected while patients temporarily are off pump or off IP.

For the following secondary safety endpoints, the incidence (percent of patients with at least 1 event) and rate will be analyzed using Prescott's exact test and Wilcoxon signed-rank test, respectively, as described above for the primary endpoint.

- suspected infusion set occlusions defined as unexplained hyperglycemia with blood glucose (SMBG) >250 mg/dL (13.9 mmol/L) that does not decrease within 1 hour (+10 minutes) following a correction bolus delivered via the pump and that leads to an infusion set change
- infusion set failures leading to premature infusion set changes due to unexplained hyperglycemia with blood glucose >250 mg/dL that does not decrease by >50 mg/dL within 1 hour (+10 minutes) following a correction bolus delivered via the pump
- premature infusion set changes for any reason and for each individual reason (infusion set kinked, came out or leaking; empty pump reservoir; infusion site pain or redness; pump occlusion alarm; suspected infusion set occlusion; other)
- severe hypoglycemic events

For the infusion set failures and premature infusion set changes, the number of events and the number of patients with events will be derived for each treatment group by infusion set catheter dwell time (≤ 24 hours, >24 and ≤ 48 hours, >48 and ≤ 72 hour, >72 hours), and overall (across over the course of approximately 72-hours of continuous infusion).

A listing of premature infusion set changes due to unexplained hyperglycemia will be generated. For each premature infusion set change due to unexplained hyperglycemia, the following information will be provided:

- whether it is an infusion set failure that meets the primary endpoint definition

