- ¹ Daytime: 0600 hours to midnight (06:00:00-23:59:59 on the 24-hour clock).
- ² Nighttime: midnight to 0600 hours (00:00:00-05:59:59 on the 24-hour clock).
- ³ Breakfast is defined as the first “Carbs” event between 4 AM and 11 AM that is associated with an “Insulin” event within ±30 minutes.
- ⁴ All eCOA non-meal related correction doses excluding those confirmed as delivered via syringe for an unexplained hyperglycemia that leads to infusion set change, will be those delivered via the pump.
- ⁵ Time in ranges within 0-1 hour and 0-2 hours after breakfast
- ⁶ Overall variability refers to the variability calculated based upon all the CGM measurements collected across all valid days for each derivation period (e.g. 4-6 weeks relative to the start of each of the randomized treatment period).

To assess the glucose control over the course of approximately 72-hours of continuous insulin infusion, the duration and percentage of time in ranges (target, hypoglycemia or hyperglycemia)

and incremental AUCs after breakfast, will be derived based upon the CGM raw data collected on each of the infusion set catheter dwell days, including Day 1 (<0 and ≥ 24 hours), Day 2 (<24 and ≥ 48 hours) and Day 3 (<48 and ≥ 72 hours), and summarized by treatment group.

The glucose reduction rate and duration of each individual hypoglycemia episode will be analyzed by an MMRM model. The MMRM model will include the fixed effects of treatment, period, and sequence as fixed effects and patient as a random effect.

The glucose reduction rate and duration of each hypoglycemia episode will be analyzed by an MMRM model. The MMRM model will include the fixed effects of treatment, period, and sequence as fixed effects and patient as a random effect.

Hypoglycemia/hyperglycemia rates as measured by CGM data will be summarized for 30 days and 1 year / 100 years (hypoglycemia <50 mg/dl and hyperglycemia >300 mg/dl only). The rate of hypoglycemia and hyperglycemia will be compared between treatment groups using Wilcoxon signed-rank test.

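### The catheter dwell-day limits in SAP 6.12 have their inequality signs reversed, so Days 1, 2 and 3 of the by-day CGM summary contain no data if the rule is followed literally

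*SAP*

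**What the plan says.** Protocol 10.3.3.3 plans time in glucose ranges and incremental AUC after breakfast from data "collected on Day 1, Day 2, and Day 3 of infusion set catheter wear and summarized by treatment group". It gives no hour limits for the days and leaves the details of the tertiary endpoints to the SAP. The amendment summary in Protocol Appendix 8 attributes this by-day analysis to an FDA request concerning treprostinil exposure over three days.

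SAP 6.12 supplies the limits. It takes "CGM raw data collected on each of the infusion set catheter dwell days" and defines the days as "Day 1 (<0 and ≥ 24 hours), Day 2 (<24 and ≥ 48 hours", and then "Day 3 (<48 and ≥ 72 hours), and summarized by treatment group".

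SAP 6.11.2 also divides wear time, for counts of infusion set failures and premature set changes. Its bins are "≤ 24 hours, >24 and ≤ 48 hours, >48 and ≤ 72 hour, >72 hours". Protocol 10.3.3.2 has the same four bins for the same counts.

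**The concern.** In all three dwell days of SAP 6.12 the lower limit carries a less-than sign and the upper limit an at-or-above sign. Joined by 'and', the two conditions exclude each other. A program written from the text would return nothing for any of the three days.

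Two things make this worth correcting although the slip is obvious. First, no other text holds the hour limits for this summary, so there is no correct statement to fall back on. Second, the Revision History describes this SAP as the third version, approved before first unblinding. If it stands, whoever programs the summary has to settle the bins informally, for an analysis that a regulator asked for.

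**Working it through.** The plan gives no figure to reproduce here. The check is set logic plus a count.

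**Inputs**
- Dwell-day limits: SAP 6.12, as quoted above.
- Comparison bins: SAP 6.11.2 and Protocol 10.3.3.2.
- Reading frequency: 288 per 24 hours (SAP 6.12), that is 24 × 60 / 5 = 288, one every 5 minutes.
- Longest wear within the planned change interval of 72 ± 4 hours (SAP 6.11.2): 72 + 4 = 76 hours.

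**Grid.** One infusion set worn from 0 to 76 hours, read every 5 minutes: 76 × 12 + 1 = 913 readings.

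**Logic.** With lower limit a and upper limit b, the SAP requires t < a and t ≥ b. Since a < b for every day, no t qualifies.

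**Counts on the grid**

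| Rule | Day 1 | Day 2 | Day 3 |
|---|---|---|---|
| As printed (t < a and t ≥ b) | 0 | 0 | 0 |
| 'and' read as 'or' | 625 | 625 | 625 |
| Signs reversed in place (t > a and t ≤ b) | 288 | 288 | 288 |
| Signs reversed and equality moved to the lower limit (t ≥ a and t < b) | 288 | 288 | 288 |

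Reading 'and' as 'or' does not rescue the text. Each day then takes everything outside its own 24 hours (913 − 288 = 625), and the days overlap.

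**Comparison with 6.11.2.** Reversing each printed sign where it stands gives >0 to ≤24, >24 to ≤48 and >48 to ≤72 hours. The cut-points are those of 6.11.2: a reading at exactly 24 hours belongs to Day 1 in both places, and one at exactly 48 hours to Day 2 in both.

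**What the reversal leaves over.** 913 − 3 × 288 = 49 readings: the one at exactly 0 hours and 48 after 72 hours (4 hours × 12). The first bin in 6.11.2 has no lower limit and so includes time 0. The 48 late readings correspond to 4 of 76 hours (5.3%) for a set worn to the end of the permitted window.

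**The case against.** The strongest reply is that this is a typographical slip with one evident meaning. The day labels, the cut-points 0, 24, 48 and 72, and the correctly signed bins in 6.11.2 all point to it, and a competent programmer would reverse the signs without asking. The summary is exploratory, and the by-day text plans only a summary by treatment group. All of this stands, and it sets the weight of the point. It does not remove the point, because the text is an operative rule and the only source of these limits.

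Three stronger readings are tempting, and the documents do not support them.

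- **That the two sets of bins would still disagree at 24 and 48 hours after correction.** They would not. Reversal in place gives the 6.11.2 cut-points exactly. A reading at 24 or 48 hours changes side only if the equality is also moved from the upper to the lower limit. That is a different repair, and it affects at most one reading per boundary.
- **That the lack of a category beyond 72 hours is an error.** Protocol 10.3.3.3 limits this analysis to Days 1 to 3 of wear, and the SAP follows it. The tables in 6.11.2 count events, so an event after 72 hours needs a category. A three-day glucose summary does not. Nor would 4 hours make a comparable fourth day: 48/288 is 17% of a day's readings, against the 70% that the SAP asks of a valid 24-hour CGM day, if that rule were applied to dwell days.
- **That glucose by wear day and failures by wear day are meant to be read jointly.** Both analyses refer to about 72 hours of infusion, but neither document says that they will be interpreted together.

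**Conclusion.** The point holds. The three dwell-day definitions in SAP 6.12 are wrong as written: each selects 0 of 913 readings on the test grid, against 288 per day once the signs are reversed. Literal execution would leave the by-day glucose summary empty.

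A reader might infer that a planned analysis would in fact be lost, or that the trial's main results are at risk. Neither follows. The intent is plain and the slip would very probably be put right in programming. The primary endpoint, the dwell-time tables in 6.11.2 and the sample size do not use these definitions. This is a minor correction, desirable rather than essential.

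The conclusion assumes that the signs in the SAP are as they appear in the text available for review. A fault in reading the PDF cannot be fully excluded, but it is unlikely: all three days show the same reversal, while the similar bins in 6.11.2 read correctly. The counts assume one reading every 5 minutes with none missing; the emptiness of the bins needs no such assumption.

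**What to change.** In SAP 6.12, replace the three definitions with:

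- Day 1: 0 to ≤24 hours
- Day 2: >24 to ≤48 hours
- Day 3: >48 to ≤72 hours

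State that time is counted from the recorded set change. This settles which end of each day is closed, places the reading at 0 hours in Day 1, and matches the cut-points in SAP 6.11.2 and Protocol 10.3.3.2.

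Optionally, add a sentence saying that readings after 72 hours lie outside this three-day summary, or that they are reported separately. This is a clarification and not part of the correction.

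The cost is one line of SAP text. No data collection, sample size or other analysis changes. Protocol 10.3.1 and SAP 6.1 require a protocol amendment only when a principal feature changes, so an SAP correction or a note in the clinical study report is enough.

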6.12. CGM Analyses

The analyses described in Section 6.12 will include data collected from first dose to last dose of study drug (i.e., open-label insulin lispro used during the lead-in period or IP used during each of the randomized treatment periods [Period I and Period II]), excluding data (if any) that are collected while patients temporarily are off pump or off study treatment.

All of the variables will be derived for the lead-in period, Period I and Period II. For the lead-in period, the variables will be derived based upon the data collected during the 2-week open-label lispro treatment period. For Period I and Period II, the variables will be derived for 0-4, 0-6, and 4-6 weeks relative to the start of each randomized treatment period, respectively. For the interstitial glucose reduction rate, treatment comparisons will be based upon the derived outcome variables for 0-6 weeks. For other variables, treatment comparisons will be based upon the derived outcome variables for 4-6 weeks.

Table ITSI.6.8 lists all numerical measures for CGM data, including all secondary and exploratory CGM outcome variables.

To ensure that the CGM outcome variables are only calculated from CGM session days with sufficient data within the 24-hour, daytime (0600 hours to midnight), or nighttime (midnight to 0600 hours) periods, the following criteria will be used to determine a valid CGM session day to be counted into the calculation for a visit: 1) minimum number of measures per day – at least 70% of the total measures that are supposed to be obtained (for example, 70% of the 288 measures for the 24-hour period or 70% of 72 measures for the nighttime period); 2) maximum allowable missing interval – no interval greater than 3 hours between non-missing measures.

Similarly, for the by-meal outcome variables, the following criteria will be used to determine a valid CGM session day for a visit: 1) minimum number of measures per day – at least 70% of the total measures that are supposed to be obtained. For example, 70% of the 24 measures for the $iAUC_{0-2hr}$ after breakfast; 2) maximum allowable missing interval – no interval greater than 20 minutes between non-missing measures for the outcome variables using ≤ 2 -hour of CGM data (including $iAUC_{0-1hr}$, $iAUC_{0-2hr}$, average glucose excursions 0-1 or 0-2 hours and time in ranges 0-1 or 0-2 hours after breakfast), and 25 minutes for other by-meal outcome variables.

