	Duration (in minutes) and percentage of time with glucose values <50, <60, and ≤70 mg/dL of hypoglycemic episodes, defined as at least 10 consecutive minutes <50, <60, and ≤70 mg/dL [2.8, 3.3, and 3.9 mmol/L]	x	x	x	x ⁵

Category	Endpoints	24-Hour	Daytime ¹	Nighttime ²	Breakfast ³
	Rate (events/patient/year and/or events/patient/30 days) and incidence (percent of patients with at least 1 event) of hypoglycemic episodes, defined as at least 10 consecutive minutes <50, <60, and ≤70 mg/dL [2.8, 3.3, and 3.9 mmol/L]	x	x	x	
Hyperglycemic Episodes					
	Duration (in minutes) and percentage of time with glucose values >180, >250, and >300 mg/dL [10.0, 13.9, and 16.6 mmol/L] and hyperglycemic episodes, defined as at least 10 consecutive minutes >180, >250, and >300 mg/dL [10.0, 13.9, and 16.6 mmol/L]	x	x	x	x ⁵
	Rate (events/patient/year and/or events/patient/30 days) and incidence (percent of patients with at least 1 event) of hyperglycemic episodes, defined as at least 10 consecutive minutes >180, >250, and >300 mg/dL [10.0, 13.9, and 16.6 mmol/L]	x	x	x	
Daily CGM Data Summary					
	Average glucose level	x	x	x	
	Median glucose level	x	x	x	
Glucose Variability and Risk Assessment					
Within-Day	CV	x	x	x	
	SD	x	x	x	
	IQR	x	x	x	
	MAGE	x	x	x	
	LBGI: frequency and extent of low BG readings	x	x	x	
	HBGI: frequency and extent of high BG readings	x	x	x	
	BGRI = LBGI + HBGI: a measure of overall variability and risks of hypo- and hyperglycemia	x	x	x	

Category	Endpoints	24-Hour	Daytime ¹	Nighttime ²	Breakfast ³
Between-day	CV	x	x	x	
	SD	x	x	x	
	MODD	x	x	x	
Overall ⁶	CV	x	x	x	
	SD	x	x	x	
	IQR	x	x	x	
	LBGi	x	x	x	
	HBGI	x	x	x	
	BGRI	x	x	x	
Highest Postprandial Glucose					
	Time from start of meal to the highest postprandial glucose level (minutes) within 3 hours after breakfast				x
	Highest postprandial glucose level within 3 hours after breakfast				x
Other					
	Duration (in minutes) of each individual hypoglycemic episode (defined as at least 10 consecutive minutes <50, <60, and ≤70 mg/dL [2.8, 3.3, and 3.9 mmol/L])	across all hypoglycemic episodes with duration at least 10 consecutive minutes			

Abbreviations: AUC = area under curve; BGRI = blood glucose risk index; CGM = continuous glucose monitoring; CV = coefficient of variation; HBGI = high blood glucose index; IQR = interquartile range; LBGi = low blood glucose index; MAGE = mean amplitude of glycemic excursions; MODD = mean of daily differences; SD = Standard deviation.

Note:

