9.1. Derivation of CGM Variables

9.2. General Derivation Specifications

All CGM variables will be derived for each patient, for each time interval of each study period (lead-in, Period I and Period II), based upon the data from valid CGM session days (Section 6.12). For Period I and Period II, the variables will be derived for 0-4, 2-6 (interstitial glucose reduction rates only), 0-6, and 4-6 weeks relative to the start of each randomized treatment period, respectively.

If any concentration below lower limit of quantification (LOQ) or above upper LOQ are identified, they will be treated as LOQ for calculation of the CGM parameters. No missing CGM values will be imputed.

Since the CGM values may not be measured at the exact same time for each day for a specific individual patient, due to device changes or gaps in usage, non-overlapping intervals ('buckets') of 5 minutes over 00:00:00 to 23:59:59 (00:00:00 to 00:04:59, 00:05:00 to 00:09:59, etc.) will be used for any derivations requiring time-matched measurements across days within a visit (e.g., mean of daily difference [MODD]).

All CGM parameters will be estimated to precision of 1 decimal place, unless stated otherwise. All CGM glucose derivations will be conducted in units of mg/dL and mmol/L.

Only readings collected from valid CGM days while patients are on pump and on IP, will be included in the derived.

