9.12. Other

The duration of each episode of hypoglycemia will be calculated as stop time – start time.

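### CGM hypoglycemic episode durations are modelled with patient as the only random effect, so the treatment standard error is too small if episodes cluster within a treatment period

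*SAP*

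**What the plan says.** SAP 6.12 sets two CGM outcomes apart: "The glucose reduction rate and duration of each individual hypoglycemia episode will be analyzed by an MMRM model". The model follows: "The MMRM model will include the fixed effects of treatment, period, and sequence as fixed effects and patient as a random effect". The remaining continuous CGM variables go to Model 2 of SAP 6.1.

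For episode duration, the records are described in Table ITSI.6.8 as taken "across all hypoglycemic episodes with duration at least 10 consecutive minutes", and SAP 9.12 defines one value per episode: "The duration of each episode of hypoglycemia will be calculated as stop time" minus start time. The comparison window comes from SAP 6.12: "For other variables, treatment comparisons will be based upon the derived outcome variables for 4-6 weeks".

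For the reduction rate the window differs: "For the interstitial glucose reduction rate, treatment comparisons will be based upon the derived outcome variables for 0-6 weeks". SAP 9.3 calculates a value for each correction bolus, and Table ITSI.6.8 refers to all such doses. SAP 9.2 states a general rule, "All CGM variables will be derived for each patient, for each time interval of each study period", and lists the intervals: "the variables will be derived for 0-4, 2-6 (interstitial glucose reduction rates only), 0-6, and 4-6 weeks". Nothing says whether boluses are averaged before modelling.

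**The concern.** Each patient receives one insulin per period, so the treatment difference has to be judged against variation between periods within a patient. A patient random intercept assumes that, given the patient, two episodes in the same period are no more alike than two episodes in different periods. If that is false, the model counts correlated episodes as independent information on treatment, and the confidence interval is too narrow.

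Period-specific variation is plausible, though the documents do not show it. Both periods start from the same reset pump settings (Protocol 5.4). The settings are then adjusted separately during the first four weeks and kept fairly stable in the last two (Protocol 5.1), which is the window compared for durations.

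At stake are the interval and p-value for episode duration, and those for secondary objective 6 if it is analysed by bolus. About half of the excess false positives would favour LY900014.

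**Working it through.** **Inputs from the documents.** The test is two-sided at 0.05 (SAP 6.1). About 42 completers are expected: 42/0.88 = 47.7, which reproduces the 48 randomized in SAP 5.2. The SAP gives no variance component, episode count or standard error for this model.

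**Assumed inputs.** Let m be the mean number of events per patient-period, and rho the patient-by-period share of within-patient variance.

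**Formula (equal counts).** Set within-patient variance to 1.

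- True variance of a patient-period mean, given the patient: rho + (1 − rho)/m.
- Variance the patient-only model uses, pooling both strata by degrees of freedom: [(1 − rho) + rho·m/(2m − 1)]/m.
- Type I error: 2·[1 − Phi(1.96/√ratio)], where ratio is the first divided by the second.

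**Example, m = 10, rho = 0.05.** True: 0.05 + 0.95/10 = 0.145. Used: (0.95 + 0.5/19)/10 = 0.0976. The ratio is 1.485 and its square root 1.22, so the reported standard error is too small by a factor of 1.22. Type I error is 10.8%.

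**Type I error at nominal 5%:**

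| m | rho 0.02 | rho 0.05 | rho 0.10 |
|---|---|---|---|
| 1 | 5.0% | 5.0% | 5.0% |
| 2 | 5.3% | 5.8% | 6.6% |
| 3 | 5.6% | 6.4% | 8.0% |
| 5 | 6.0% | 7.7% | 10.5% |
| 10 | 7.3% | 10.8% | 16.5% |
| 20 | 9.7% | 16.6% | 26.2% |
| 40 (boluses over weeks 0–6, only if analysed by bolus) | 14.4% | 26.0% | 38.8% |

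At rho = 0 the error is 5.0% for every m. Type I error reaches 10% at rho of about 0.16 (m = 3), 0.09 (m = 5), 0.043 (m = 10), 0.021 (m = 20) and 0.011 (m = 40).

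**Unequal counts.** Simulation used 4000 null trials per cell, 21 + 21 patients, Poisson counts with gamma patient means (zeros included) and normal data. Under the planned model, for rho 0.02 / 0.05 / 0.10, it gave:

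- m = 3: 5.4 / 7.9 / 9.7%
- m = 5: 6.8 / 10.0 / 14.7%
- m = 10: 8.7 / 13.4 / 20.6%
- m = 20: 12.6 / 22.0 / 32.4%

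At rho = 0 it gave 4.9–5.7%. Over all cells, a model with a nested patient-by-period effect gave 3.4–5.9%, and patient-period means gave 3.9–5.4%. Degrees of freedom of patients with both periods minus 2 stood in for Kenward-Roger in both.

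**What m might be.** SAP 9.6 has a hypothetical patient with 135 readings at or below 70 mg/dL out of 3078. At 288 readings a day that is 3078/288 = 10.7 days. SAP 9.7 requires at least three readings per episode, so there are at most 135/3 = 45 episodes. At an assumed 6–12 readings each, with all low readings falling in episodes, there are 11–22, or 15–29 scaled to 14 days. This is an illustration, not data, and the lower thresholds would give fewer.

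**The case against.** The best counter-argument is that the SAP may intend one value per patient-period for both outcomes. The general rule in SAP 9.2 covers all CGM variables, and SAP 6.12 speaks of derived outcome variables for duration as well. The word individual may only separate episode length from total time low, which has its own row in Table ITSI.6.8. Footnote 2 of Table ITSI.6.2 waives a baseline requirement, which fits a per-patient summary. SAP 6.11.10 also uses patient as the random factor for vital signs, although SAP 6.1 gives them an unstructured covariance, so the phrase may be shorthand. On the one-value reading the problem disappears.

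For the reduction rate this stands: the unit is open, and with one value per patient-period the model is correct. For duration it does not displace the plainer reading. The SAP names each episode as the thing analysed and gives no averaging rule. When it wants a period mean it says so, as for time until infusion set change in SAP 6.11.2.

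The defaults do not rescue the model. The unstructured covariance in SAP 6.1 is tied to scheduled visits, and its homogeneous compound-symmetry fallback is in effect a patient intercept. Kenward-Roger does not supply a missing variance component.

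It is also fair that the size rests on assumptions, that durations are not normal, and that the consequence is limited. Episode duration is not among the 20 listed endpoints, secondary and exploratory tests carry no multiplicity control (SAP 6.5), and the primary Wilcoxon signed-rank test (SAP 6.11.1) is unaffected.

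**Conclusion.** The point holds, conditionally. For episode duration, the model as written understates the treatment standard error whenever some patient-periods contain more than one episode and patient-by-period variance is above zero. If either condition fails, the standard error is right. The inflation is small with few episodes (5.3–6.6% at m = 2) and material with many (9.7–26.2% at m = 20), for assumed rho of 0.02 to 0.10 and equal counts. Unequal counts mostly make it worse. The documents cannot place the trial within that range.

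For secondary objective 6 no error is shown. The gap is that the unit of analysis is unstated, and a bolus-level analysis would have the same fault. This should be fixed before unblinding, but it does not bear on the trial's main conclusion.

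**What to change.** In SAP 6.12:

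1. For episode duration, at each glucose threshold, add a random patient-by-period effect nested in patient, with Kenward-Roger degrees of freedom. If a per-period mean was intended instead, say so; the present model then stands.
2. State the unit of analysis for the glucose reduction rate. If it is one value per patient-period, keep the model. If it is the bolus, add the same nested term, including in the starting-glucose sub-intervals and the per-unit-dose version.
3. If the nested model does not converge, analyse one mean per patient-period with treatment, period, sequence and random patient. Leave out a baseline covariate, so that patients with no lead-in event stay in, as footnote 2 of Table ITSI.6.2 intends.

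The cost is a few lines of text and one extra RANDOM statement, with no new data. If patient-by-period variance is truly zero, the nested model is slightly conservative in the simulations (type I error 3.5–3.9%), with intervals 3–6% wider than planned. The means analysis would then cost more, with intervals 20–39% wider, because it weights patients with few and many events equally. That is why it is only the fallback.
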